13.0 Withdrawal of Subjects*

13.1 Subjects will be withdrawn from the research without their consent if they become intolerant to the treatment and/or the researchers determine that they are too nervous, anxious to continue.

13.2 Orderly termination will proceed at the end of study period for all subjects. This will simply mean no further visits and no further data collection will occur.

13.3 Subjects may voluntarily terminate their participation in the research at any time by informing a member of the research team. A subject may partially withdraw from the study after the initial treatment and control have been administered or even during administration if the participant is unable or unwilling to continue or do the follow up visits.

If a subject withdraws or is withdrawn from the study prior to completion, further data collection will be stopped. However, partial data already collected will be used for analysis.

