8.0 Study Endpoints*

8.1 Primary endpoints: Participation in the study will end 12 months after the baseline visit or if the patient elects to be removed from the study, whichever comes first.

PROTOCOL TITLE: The Effect of Abobotulinum Toxin A on the Symptoms of Raynaud's Phenomenon, a Double-Blind Randomized Placebo-Controlled Trial

- 8.2 Primary and secondary safety endpoints: adverse reaction to the abobotulinum toxin A solution. If a participant develops a reaction, he or she will be given the option to withdraw but will not be required to withdraw, unless life threatening.

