9.2 Timeline

- Subject visits
 - The abobotulinum toxin A solution and saline solution will be prepared the same day as the subject's baseline visit
 - Baseline Visit
 - a. Minute 00-20:
 - i. Screening and consent process in screening room
 - b. Minute 20-40:
 - i. Assessment of baseline Raynaud's symptoms via Baseline Case Report (attached) and photographs will be taken of both hands
 - ii. Administration of abobotulinum toxin A solution and normal saline solution
 - c. Minute 40-60:
 - i. Review post-procedure instructions and how to complete Brief Follow-up Case Reports. Observe subject for any adverse reaction.
 - 48-hour follow-up phone call:

[figure not shown]
PROTOCOL TITLE: The Effect of Abobotulinum Toxin A on the Symptoms of Raynaud's Phenomenon, a Double-Blind Randomized Placebo-Controlled Trial

- a. Minute 0-5:
 - i. Brief phone call to assess for any adverse reactions.
- 1-month (+/- 8 days) Follow-up
 - a. Minute 00-15:
 - i. Assessment of Raynaud's symptoms via Follow-up Case Report (attached) and photographs will be taken of both hands
- 3-month (+/- 15 days) Follow-up
 - a. Minute 00-15:
 - i. Assessment of Raynaud's symptoms via Follow-up Case Report (attached)
- 6-month (+/- 15 days) Follow-up
 - a. Minute 00-15:
 - i. Assessment of Raynaud's symptoms via Follow-up Case Report (attached) and photographs will be taken of both hands
- 12-month (+/- 15 days) Follow-up
 - a. Minute 00-15:
 - i. Assessment of Raynaud's symptoms via Follow-up Case Report (attached) and photographs will be taken of both hands
- Subject surveys
 - Months 0-3:
 - a. Every week the subjects will be asked to complete the Brief Follow-up Case Report either online or on a paper version given to the subject.
 - Months 4-12
 - a. Every month the subjects will be asked to complete the Brief Follow-up Case Report either online or on a paper version given to the subject
- Solution preparation

PROTOCOL TITLE: The Effect of Abobotulinum Toxin A on the Symptoms of Raynaud's Phenomenon, a Double-Blind Randomized Placebo-Controlled Trial

- 300 unit vials of abobotulinum toxin A will be reconstituted with 10 ml of non-bacteriostatic normal saline yielding a final concentration of 30 units per 1 ml.
- The solutions will be drawn up in 1 cc syringes utilizing a 25g needle by [name]. The needle will then be replaced with a capped 30g ½ inch needle.

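### A patient removed without consent after the single injection session has all later data collection stopped, although no dosing remains to discontinue (sections 13.1 and 13.3)

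*Combined protocol and SAP*

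**What the plan says.** Section 13.1 makes removal mandatory on two grounds. The first is tolerance: "Subjects will be withdrawn from the research without their consent if they become intolerant to the treatment". The second is a staff judgement that "the researchers determine that they are too nervous, anxious to continue". Neither ground is defined further.

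The closing paragraph of 13.3 treats voluntary and imposed withdrawal alike: "If a subject withdraws or is withdrawn from the study prior to completion, further data collection will be stopped". The next sentence keeps whatever was collected up to that point for analysis. No exception is made for safety follow-up or for the remaining outcome visits.

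Section 9.2 lists dosing once, at minutes 20 to 40 of the baseline visit: "Administration of abobotulinum toxin A solution and normal saline solution". No later dosing appears. Follow-up then runs to 12 months, with a 48-hour call, visits at 1, 3, 6 and 12 months, and surveys that are weekly for three months and monthly afterwards.

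Section 8.2 sets the safety endpoint: "Primary and secondary safety endpoints: adverse reaction to the abobotulinum toxin A solution". It also has its own rule for a participant who reacts: "he or she will be given the option to withdraw but will not be required to withdraw, unless life threatening".

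**The concern.** In a trial with repeated dosing, taking a patient off treatment can protect that patient. Here the full dose is in both palms before the baseline visit ends. Once it is, the only thing that removal can stop is the collection of information, and 13.1 allows this for a patient who might be willing to carry on.

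The patients affected are not a random subset. They are picked out by how they tolerated the injections, and a patient removed for a reaction has already had the event that 8.2 names as the safety endpoint. Two things are at stake: the remaining RCS, VAS Pain, QuickDASH, ulcer and attack data for that patient, and the later course of the reaction, to the extent that the study would otherwise have recorded it.

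**Working it through.** **Step 1. The sections side by side, by when and why removal happens.**

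- *During the injections.* Section 9.2 places ten injections in each palm. Stopping partway, for intolerance or anxiety, does spare exposure. Stopping is sensible here, but 13.3 still ends follow-up of a partly dosed patient.
- *After the injections, reaction not life threatening.* If intolerance in 13.1 covers this case, 13.1 forces removal while 8.2 leaves the choice to the patient. The two sections conflict.
- *After the injections, reaction life threatening.* Sections 8.2 and 13.1 agree on withdrawal. Section 13.3 then stops data collection in the patient with the gravest reaction.
- *After the injections, judged too nervous.* Only short visits and surveys remain, and no exposure is avoided.

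In every case after dosing, 13.3 stops observation and nothing else.

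**Step 2. What one removed patient loses.** Inputs from 7.1, 9.2 and 11.1: four visits after baseline; about 13 weekly surveys in months 0 to 3 and 9 monthly surveys in months 4 to 12; between-hand tests after baseline at 1 and 3 months; a within-group test from 1 to 3 months that needs both values.

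| Removed | Visits lost | Surveys lost (about) | Analyses without this patient |
|---|---|---|---|
| At the 48-hour call | 4 | 13 + 9 = 22 | 1-month, 3-month, and 1-to-3-month change |
| Just after "1-month (+/- 8 days) Follow-up" | 3 | (13 − 4) + 9 = 18 | 3-month, and 1-to-3-month change |

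These are losses of symptom outcomes. Section 9.2 describes only two scheduled contacts as checks for adverse reactions: the observation at the end of the baseline visit and the 48-hour call. The later visits and surveys are described as Raynaud's assessments, and the forms they use are attachments that cannot be seen. Loss of later adverse-event information is therefore conditional on the study otherwise capturing it, for example through a call to the clinic (9.2) or on the Adverse Event Form (9.3).

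**Step 3. Cost in power.** Inputs from 11.2: difference 2, SD 1.92, so d = 2/1.92 = 1.04; alpha 0.05, two-sided (11.1); power 0.80. The planned test is an independent-samples t-test. With n hands per arm, power comes from the noncentral t distribution with 2n − 2 degrees of freedom and noncentrality d × √(n/2).

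- The plan's own figure: solving for power 0.80 gives n = 15.53, rounded up to 16 hands per arm. That is 16 patients when each gives one hand to each arm, so the stated number reproduces.
- n = 16: noncentrality 1.04 × √8 = 2.94, 30 degrees of freedom, power 0.812.
- n = 15: noncentrality 1.04 × √7.5 = 2.85, 28 degrees of freedom, power 0.785.

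One removal costs 0.812 − 0.785 = 0.027. The plan gives no correlation between a patient's two hands. If a paired test were used, the same loss would be 0.785 to 0.755 at an assumed correlation of 0, or 0.973 to 0.962 at an assumed correlation of 0.5.

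**Step 4. Balance.** Under 9.1 each patient has one toxin hand and one saline hand. A removal takes both, so the arms stay equal in number.

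**The case against.** The case for leaving the text alone has four parts.

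- *The grounds in 13.1 may be meant for the injection session.* Being too anxious to go on fits a person facing twenty needle insertions better than one facing a 15-minute visit, and 13.3 itself mentions stopping during administration. This is a fair reading, and removal at that stage does spare exposure. But 13.1 does not limit itself to the session, and 13.3 stops follow-up whenever removal occurs.
- *Section 8.2 already governs reactions.* If it overrides 13.1, forced removal for a reaction is confined to life-threatening events and the conflict disappears. The data stop does not: it then applies to the patients whose course matters most.
- *The triggering reaction is kept.* This stands. Data collected before removal are analysed, and the endpoint in 8.2 is the occurrence of a reaction, with no measure of duration. Only the later course is at risk.
- *Patients may telephone the clinic.* They may, but nothing says that a call after removal would be recorded, and 13.3 points the other way.

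A reader might infer more than the documents support:

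- *That the rule biases the comparison.* No removal rate is given, both hands leave together, and neither the size nor the direction of any bias can be derived.
- *That adverse-event follow-up is certainly lost at every removal.* Step 2 shows why this is only conditional.
- *That removal hides whether the muscle weakness in 14.1, which may last six weeks, resolves.* The 1-month window closes by about day 39 (31 + 8), before day 42. The window for "3-month (+/- 15 days) Follow-up" opens no earlier than about day 74 (89 − 15). Retained patients therefore have no visit near week six either, and the 3-month visit is not described as assessing weakness.
- *That the safety review at 8 subjects (12.1) is undermined.* One patient in eight is arithmetic on an assumed removal. The review lists symptom measures rather than adverse events, and the plan does not say which 8 subjects are counted.

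**Conclusion.** The point holds as a defect of wording with a cheap remedy. As written, a patient removed without consent after dosing loses all remaining scheduled outcomes, with no protection gained in return. The later course of the reaction is lost as well, if it would otherwise have been captured. The conflict between 13.1 and 8.2 exists only if intolerance extends to reactions that are not life threatening; the protocol leaves the term undefined.

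The loss is conditional on a removal taking place. One removal from 16 patients lowers power from about 0.81 to 0.79 under the plan's own assumptions. If more than 16 are dosed the cost could be smaller, but 20.2 and 23.2 differ on whether the surplus over 16 covers dropout or only screening failure. The weight of the point lies in outcome and safety information from patients selected by tolerance, not in power or a demonstrated bias. The change should be made, but the analysis does not stand or fall on it.

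**What to change.** - **13.1:** define intolerance, limit the section to stopping any injections still to be given, and align it with 8.2 so that a participant whose reaction is not life threatening decides whether to leave.
- **13.3:** separate stopping injections from leaving follow-up. Unless the participant withdraws consent, continue the scheduled visits and surveys to 12 months. Section 9.2 already allows evaluation by phone at 1 and 3 months for those who cannot attend.
- **Open reactions:** state that any reaction present when injections are stopped, or when a patient would have been removed, is followed on the existing Adverse Event Form until it resolves.

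The cost is protocol wording, possibly matching consent and HIPAA wording, and a few follow-up contacts with patients who would otherwise have been removed. A participant who wishes to leave can still do so at any time.

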14.0 Risks to Subjects*

14.1 There is no major anticipated risk associated with the study. However potential risks to the subject include:

- Discomfort and pain upon injection and infiltration of abobotulinum toxin A or normal saline
- Temporary muscle weakness that may last 6 weeks
- Negligible bleeding or bruising

PROTOCOL TITLE: The Effect of Abobotulinum Toxin A on the Symptoms of Raynaud's Phenomenon, a Double-Blind Randomized Placebo-Controlled Trial

- Minimal risk of infection (<1%)¹⁶
- Allergy to abobotulinum toxin A solution (<1%)
- Furthermore, true allergy to abobotulinum toxin A is extremely rare.¹⁷

15.0 Potential Benefits to Subjects*

15.1 Potential benefits are not guaranteed to subjects but include:

- Relief from Raynaud's phenomenon symptoms
- Free treatment for their Raynaud's phenomenon

16.0 Vulnerable Populations*

16.1 This study does not involve individual who are vulnerable to coercion or undue influence.

17.0 Community-Based Participatory Research*

17.1 This is not community-based participatory research.

18.0 Sharing of Results with Subjects*

18.1 There are no plans to share results with participants.

19.0 Setting

19.1 Research will be conducted at UCF Health:

- Potential subjects will be identified and recruited at both the UCF Health clinic in Lake Nona and the UCF Health clinic on [name]
- Screening, enrollment, initial/baseline study, and follow up study visits will take place at the UCF Health clinic in Lake Nona.
- There will not be a community advisory board.

20.0 Resources Available

20.1 [name] has significant prior experience conducting research, knowledge of the regulations and customs at UCF Health, and works regularly with patients performing dermatologic surgery. All injections will be administered by [name]. [name] has extensive experience conducting clinical research. In addition, the medical students involved in the project will be able to help significantly. Through the FIRE project [name] will be able to assist with data analysis.

20.2 Resources available to conduct research:

- The study's small sample size of 20 subjects to be enrolled in order to have 16 subjects complete the study makes it likely that the required number of participants will be recruited in less than 8 months. Drs. [name] and [name] see at least this number of patients with Raynaud's phenomenon annually. In addition, the rheumatologists at UCF Health see at 3 to 4

PROTOCOL TITLE: The Effect of Abobotulinum Toxin A on the Symptoms of Raynaud's Phenomenon, a Double-Blind Randomized Placebo-Controlled Trial

times as many patients with Raynaud's phenomenon. Finally, recruiting through the local dermatology society and advertising should supplement the numbers needed to complete the study.

- Research will be conducted during [name] administrative time or on the weekend.
- The study will be conducted at the UCF Health Clinic, see section 19. Setting.
- While the chances of a research related injury are extremely rare, participants will be required to have health insurance in order to participate in this study. Treatment for research related injury will be made available, however costs associated with this treatment will be billed to the participant's insurance company. Costs not covered by participant's insurance company will be the subject's responsibility. (see Consent Form attached)
- All individuals assisting in the research study will be provided a copy of the IRB-approved protocol and given the opportunity to meet with the principal investigator before recruitment begins. The principal investigator, [name], will be responsible for informing all research staff of their research-related duties during a personal meeting or via phone or email. The contact information of the principal investigator and co-principal investigator will be distributed to all research staff and the subjects.

21.0 Prior Approvals

21.1 Approval from the medical director and the HIPAA privacy officer of UCF Health will be obtained prior to commencing research.

22.0 Recruitment Methods

22.1 The research team will start recruitment shortly after IRB approval and the abobotulinum toxin A has been received. Patients with a diagnosis of Raynaud's phenomenon will be recruited from the UCF Health Clinic during a patient's visit (medical records will not be searched for patients with a diagnosis of Raynaud's phenomenon) and through advertising on the UCF Health website and within the UCF Health clinic.

22.2 The primary source of subjects will be patients at the UCF Health Clinic and people in the greater Orlando area. This represents a large pool of potential subjects from which to recruit.

22.3 [name] and [name] will rely on prior labs, pathology reports, and physical examination to determine if the participant has a diagnosis of Raynaud's phenomenon.

22.4 An e-mail and within clinic advertisement may be used to recruit patients (see attached Advertisements). This is a small paragraph describing the study. This text may be displayed in the UCF Health clinic, to other providers at UCF Health or members of the local dermatology society. In addition, a similar small

PROTOCOL TITLE: The Effect of Abobotulinum Toxin A on the Symptoms of Raynaud's Phenomenon, a Double-Blind Randomized Placebo-Controlled Trial

paragraph describing the study will be posted on the UCF Health website (see attached Advertisements).

22.5 Participants will not be compensated for their time.

23.0 Local Number of Subjects

23.1 We plan to enroll approximately 20 subjects.

23.2 We anticipate most subjects that enrolled to be successfully screened. There may be a few subjects that will fail screening due to failing urine pregnancy testing. Given this, it may be that 18 to 20 subjects need to be enrolled and screened to obtain 16 eligible subjects.

24.0 Provisions to Protect the Privacy Interests of Subjects

24.1 Subjects will be in the same general vicinity during study and will be recruited from UCF Health Clinic. Therefore, there will be the possibility that participants may know and recognize each other.

24.2 Prior to enrollment subjects will be made aware of this possibility and if unacceptable, will be given the option to decline to participate.

24.3 All investigators will have access to all of the information collected on the subjects. The "Subject ID Assignment Log" will be kept in a separate folder so that investigators will only have access to identifiable information if needed for data entry or if there is a data discrepancy. Only de-identified data will be exported and used for data analysis.

25.0 Compensation for Research-Related Injury

25.1 While the chances of a research related injury are extremely rare, participants will be required to have health insurance in order to participate in this study. Treatment for research related injury will be made available, however costs associated with this treatment will be billed to the participant's insurance company. Costs not covered by participant's insurance company will be the participant's responsibility.

26.0 Economic Burden to Subjects

26.1 Subjects have to give his or her time (approximately 2.5 hours) and bear any transportation costs (gas, tolls, etc.). If the subject's health insurance does not cover the costs for treatment related injury, the subjects will be billed for the treatment. There are no other expected costs that subjects will incur as a result of participating in the study.

27.0 Consent Process

27.1 Consent process:

PROTOCOL TITLE: The Effect of Abobotulinum Toxin A on the Symptoms of Raynaud's Phenomenon, a Double-Blind Randomized Placebo-Controlled Trial

- The consent process will take place in person at the UCF Health clinic in Lake Nona.
- Subjects will be given the option of picking up the consent and HIPAA authorization prior to participation to discuss with their primary care physician, significant other, etc., to help minimize the possibility of coercion or undue influence. Subjects will be able to wait however long they desire after obtaining the study information and before signing the consent and HIPAA authorization. However, if the study is completed before the subject chooses to sign the consent then they will not be allowed to participate.
- Subjects may voluntarily terminate their participation in the research at any time by informing a member of the research team. Other than the initial informed consent no other formal process will be done to document ongoing consent.
- The UCF "SOP: Informed Consent Process for Research (HRP-090)" will be followed.
- The consent process and HIPAA authorization will be documented in writing. The investigator will describe the details of the study and answer any questions the subject may have about the study. Subjects will be given an informed consent and HIPAA authorization for the study and the primary investigator's contact information. Those subjects who express interest in the study will be required to sign the Informed Consent form and HIPAA authorization to ensure that there is no coercion in the study.

28.0 Process to Document Consent in Writing

- 28.1 The UCF "SOP: Written Documentation of Consent (HRP-091)" will be followed.
- 28.2 All participants will be required to complete and sign the informed written consent document (see attached) to ensure that there is no coercion in the study. The informed consent documents will be signed both by the participant and by the principal investigator (see attached "Informed Consent").

